8.2.2.3. Cutoff for HRG Expression

HRG expression value will be summarized by treatment group for overall, HRG-high, and HRG-low group with summary statistics. The distribution of HRG values will be plotted with histogram and normal curves.

HRG expression values will be dichotomized at alternative cutoffs to form new HRG-high and HRG-low groups. Analysis of PFS and OS specified in Section 8.2.1 and Section 8.2.2.1 will be performed for newly classified HRG high and low groups at alternative cutoffs. The results will be used to select optimum HRG cutoff.

8.2.3. Analysis of Exploratory Efficacy Variables

Exploratory efficacy endpoints include duration of response, time to response, time to disease progression, and duration of SD.

8.2.3.1. Duration of Response

The distribution of duration of response as defined in Section 5.1.4.1 of this SAP will be presented as Kaplan Meier plot, together with response duration quartiles for responding subjects (PR or CR). Median time to response will be estimated along with two-sided 80% and 95% CIs using Kaplan-Meier methods

8.2.3.2. Time to Response

The distribution of time to response as defined in Section 5.1.4.2 of this SAP will be presented as Kaplan Meier plot, together with response duration quartiles for responding subjects (PR or CR). Median time to response will be estimated along with two-sided 80% and 95% CIs using Kaplan Meier methods.

8.2.3.3. Time to Disease Progression

Median time to disease progression will be estimated along with two-sided 80% and 95% CIs using Kaplan-Meier methods by treatment. In addition, summary statistics for 25% and 75% percentiles will be estimated using Kaplan-Meier methods.

8.2.3.4. Duration of Stable Disease

The distribution of duration of stable disease as defined in Section 5.1.4.4 of the SAP will be presented as Kaplan Meier plot, together with response duration quartiles for responding subjects with the best response of stable disease. In addition, median duration of stable disease will be estimated along with two-sided 80% and 95% CIs using Kaplan-Meier methods.

8.2.4. Sensitivity and Subgroup Analysis

8.2.4.1. Sensitivity Analysis

Sensitivity analysis for PFS will be performed by including both RECIST progression disease and clinical progression as PFS events. If HRG cutoff is changed during subject enrollment and stratification, the subject HRG status (High versus Low) will be redefined

using the changed HRG cutoff into new HRG high and low cohorts. Statistical analysis for PFS and key secondary endpoints will be conducted for the new HRG cohorts as a sensitivity analysis.

8.2.4.2. Subgroup Analysis

The subgroup analyses for PFS and OS specified in Section **Error! Reference source not found.** and Section **Error! Reference source not found.** will be performed for the subgroups below if data warrants:

- Age (≤ 65 , > 65 yrs)
- Sex (Female, Male)
- Race (White, Non-white)
- HPV status (Positive, Negative)
- HRG subgroups (alternative cutoffs)
- Primary tumor site (oral cavity, oropharynx, hypopharynx, and larynx)
- ECOG performance status (0, 1)
- Platinum-based therapy (cisplatin carboplatin; n.b., subjects treated with both will be excluded)
- Tumor grade (well- or moderately differentiated, poorly differentiated)
- Previous treatment (neoadjuvant chemotherapy, radiochemotherapy)
- Baseline FACT-H&N total score (\leq median, $>$ median)

A Cox proportional hazards regression with treatment as the only covariate will be applied. Forest plots will be presented for both PFS and OS.

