  25. Receiving yellow fever vaccine or live attenuated vaccines (for subjects receiving carboplatin)
  26. Presence of hemorrhagic tumors (for subjects receiving carboplatin)
  27. Prophylactic use of phenytoin or fosphenytoin (for subjects receiving cisplatin or carboplatin)
- 

Dosage Form, Dose and  
Route of Administration:

Patritumab

Placebo lyophilisate will be diluted in an identical manner in 8 mL water.

The order of IV administration will be:

1. Patritumab or placebo
  - Patritumab/placebo initial loading dose [REDACTED] over 60 minutes ( $\pm$  10 minutes) followed in cycle 2 and beyond with a maintenance dose of [REDACTED] over 60 minutes ( $\pm$  10 minutes) every three weeks
    - Infusion time can be extended to a maximum of 120 minutes for subjects unable to tolerate the 60 minute infusion
2. Cetuximab
  - Cetuximab initial dose at 400 mg/m^2 IV as a 2-hour infusion on Week 1, followed by 250 mg/m^2 over 60 minutes weekly, plus

One hour after the end of the cetuximab administration infuse with either:

3. Cisplatin OR carboplatin selected at the discretion of the Investigator.
    - Cisplatin at 100 mg/m^2 IV infused over 1 hour, every three weeks up to a maximum of 6 cycles
      - Pretreatment hydration with 2 liters of fluid prior to a cisplatin infusion is recommended and should adhere to institutional standards.
-

Adequate hydration and urinary output must be maintained during the following 24 hours. Other pretreatments such as anti-emetic prophylaxis and post-treatments such as hydration are up to the discretion of the Investigator.

OR

- Carboplatin, at AUC 5 IV bolus over 30 to 60 minutes, every 3 weeks for a maximum of 6 cycles. The carboplatin dose will be calculated using the Calvert formula:
  - AUC 5 is the target
  - Carboplatin Dose (mg) = 5 x ([glomerular filtration rate] GFR + 25)
  - Estimated serum creatinine clearance (mL/min) calculated using the modified Cockcroft-Gault equation ([Appendix 17.1](#)) can also be used as an estimate for GFR
  - The carboplatin dose is required to be re-calculated for every dosing based on the current GFR (or creatinine clearance as an estimate of GFR as per the protocol)
  - Pre- and post-treatments are up to the discretion of the investigator

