#### **5.1.7. Guidelines For Dose Modifications**

For those subjects who continue treatment, the Investigator will evaluate which hematological and/or non-hematological toxicities are attributed to which drug(s), and adjust the dose of one or more of the drugs as recommended below.

If a subject experiences an unacceptable toxicity to cisplatin, the Investigator will be able to withhold drug, reduce dose, or switch to carboplatin. If the Investigator chooses to start treatment with carboplatin, then carboplatin will be administered throughout the study. If a subject also experiences an unacceptable toxicity to carboplatin, then carboplatin treatment will be withheld or dose reduced.

Subjects with unacceptable toxic effects of one of the study drugs will receive only the tolerated drugs until disease progression.

- If patritumab/placebo needs to be discontinued, the subject will be withdrawn from the study
- In subjects whose cisplatin or carboplatin therapy is discontinued, reduced, or delayed, the patritumab and cetuximab will be continued and subjects will continue to undergo tumor assessments at 6 week intervals until disease progression or unacceptable toxicity
- In subjects whose cetuximab dose is discontinued, reduced, or delayed, the patritumab will be continued. Cisplatin or carboplatin will be administered for a maximum of 6 cycles
- In subjects whose cetuximab and cisplatin or carboplatin are either discontinued or delayed, patritumab will be continued as monotherapy

In addition to the recommendations provided below, please refer to the respective current prescribing information for detailed recommendations on managing suspected toxicities, for guidance on withholding, dose reductions, and discontinuation. If toxicities occur, it is up to the discretion of the Investigator to dose reduce or withhold one or more medications until recovery or resolution of the AE to Grade 0 or 1.

In individual cases, if a subject discontinues study drugs for an extended time period, the subject may restart study drugs at the discretion of the investigator after discussion with the Sponsor and CRO's medical monitors.

Investigators may contact the Sponsor's medical monitor to discuss any question regarding dose modification or discontinuation of study drugs.

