**Table 5.5: Cisplatin Dose Modifications and Discontinuations\* for Toxicities**

Toxicity	Dose Modification/Discontinuation
Hematological	A repeat course should not be given until circulating blood elements are at an acceptable level (ie, platelets $\geq 100 \times 10^9/L$ , white blood cells $\geq 4 \times 10^9/L$ )
Febrile neutropenia/infection	The first episode of febrile neutropenia or infection will result in reduction by 20% of cisplatin dose. If there is a second episode, despite dose reduction, the subject must receive prophylactic antibiotics during subsequent cycles. If there is a third episode, the subject will be withdrawn from study.
Neutropenia	Grade 2 or 3: cisplatin treatment delay until < Grade 1. Grade 4: cisplatin treatment delay until < Grade 1; dose reduction of all further doses of cisplatin by 20%.
Nephrotoxicity	A repeat course of cisplatin should not be given until the serum creatinine is below 1.5 mg/100 mL, and/or the urea is below 25 mg/100 mL
Thrombocytopenia	Grade 1: cisplatin treatment delay until platelets $\geq 100,000/mm^3$ . $\geq$ Grade 2: cisplatin treatment delay until platelets $>100,000/mm^3$ , dose reduction of all further doses of cisplatin by 20%

Toxicity	Dose Modification/Discontinuation
Organ Toxicity	Grade 2: Delay chemotherapy until $\leq$ Grade 1. $\geq$ Grade 3 or more: Delay chemotherapy until $\leq$ Grade 1; dose reduction of all further doses of cisplatin by 20%. Do not delay or reduce cisplatin dose if there are asymptomatic increases in transaminases, cetuximab-induced skin reactions, and subclinical side effects (e.g. nausea, vomiting, alopecia, altered taste).
Ototoxicity	Criteria for hearing testing
Neuropathy	In case of sensory neuropathy $\geq$ Grade 2, change cisplatin to carboplatin

Note: Please refer to the cisplatin package insert for additional information on potential toxicities and their management. When cisplatin is administered in combination with other agents such as cetuximab, refer to their respective product information. \*If events do not recover within 3 weeks, discontinue cisplatin treatment.

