8.2.1. Analysis of Primary Efficacy Variables

The primary efficacy endpoint is PFS as defined in Section 5.1.1 of this SAP. Progression will be determined based on the investigators' assessment.

The primary efficacy analysis will be the comparison of PFS between the patritumab arm and the control arm in HRG-high stratum of the FAS using the stratified log-rank test. For a description of the handling of censored data for efficacy endpoint PFS, see Section 5.1 above.

The testing hypotheses to compare PFS for the patritumab arm versus the control arm will be performed in two sequential steps (Freidlin 2012 et al). In step 1, the null hypothesis that PFS is the same for both arms in the HRG high stratum of FAS is tested at the one-sided 0.10 significance level. If this test in step 1 does not reject the null hypothesis, then in step 2A, the null hypothesis that PFS is the same for both arms in the FAS (HRG high stratum + low stratum) will be tested at the one-sided 0.05 significance level. If the test in step 1 is rejected, then in step 2B, the two-sided 80% confidence interval (CI) for hazard ratio (HR) of PFS in the HRG low stratum of the FAS will be estimated.

The comparison of PFS between the patritumab arm and the control arm will be performed using a log-rank test stratified by the stratification factors.

Hypothesis testing for superiority with regard to PFS will be performed with a 1-sided hypotheses setting.

Suppose that $S_A(t)$ and $S_P(t)$ are the cumulative survival functions for PFS in patritumab and control treatment groups, respectively. The null hypothesis H_0 with PFS:

$$H_0: S_A(t) = S_P(t) \text{ for all } t \geq 0 \text{ (identical survival functions for both groups)}$$

will be tested against the 1-sided alternative hypothesis H_A :

$$H_A: S_A(t) \geq S_P(t) \text{ for all } t \geq 0 \text{ and } S_A(t) > S_P(t) \text{ for at least some } t > 0$$

(improvement in PFS in the patritumab group over the control group)

The stratified log-rank test will be conducted using SAS PROC LIFETEST where the STRATA statement will include the treatment group and the stratification factors [HPV (positive vs other) and HRG (high vs. low, only for the FAS) at randomization]. The 1-sided p-value will therefore be obtained and H_0 will be rejected if p-value \leq the pre-specified 1-sided alpha.

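### The platinum subgroup drops subjects who switched from cisplatin to carboplatin after randomisation, which can bias the cisplatin-row hazard ratio in either direction if switching differs by arm

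*SAP*

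**What the plan says.** SAP 8.2.4.2 lists eleven subgroup factors for PFS and OS, each analysed with a Cox model containing treatment alone. One entry is the platinum agent, cisplatin or carboplatin, with the note that "subjects treated with both will be excluded". The PFS table is 15.2.1.3, labelled Full Analysis Set, and its shell reports medians by arm as well as the hazard ratio. SAP 6.1.1 defines that set as everyone randomised, analysed as randomised. SAP 7.6 calls the subgroup analyses exploratory.

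The protocol shows who receives both agents. The starting agent is not randomised: "Cisplatin OR carboplatin selected at the discretion of the Investigator" (Protocol Synopsis, dosing). Nor is it a stratification factor; SAP 8.2.1 lists only "HPV (positive vs other) and HRG (high vs. low, only for the FAS) at randomization". Protocol 5.1.7 allows a change during treatment: "If a subject experiences an unacceptable toxicity to cisplatin, the Investigator will be able to withhold drug, reduce dose, or switch to carboplatin". Table 5.5 adds a directed change for sensory neuropathy, "change cisplatin to carboplatin". For a subject who starts on carboplatin, Protocol 5.1.7 says "then carboplatin will be administered throughout the study".

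SAP 8.2.4.1 (sensitivity analyses) does not mention platinum switching, and no other section handles switchers differently.

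**The concern.** The other ten factors in SAP 8.2.4.2 are fixed before treatment starts. Platinum agent is the only one that depends on what happens afterwards. To be excluded, a subject must start cisplatin, stay progression-free and on treatment long enough to develop toxicity, and then be switched. Removing these subjects conditions on an outcome of treatment and on time at risk, so the arms left in the cisplatin row are no longer the randomised arms among cisplatin starters.

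At stake is how the cisplatin-row hazard ratio and medians are read, and with them any impression that the patritumab effect depends on the platinum partner.

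**Working it through.** **The plan's own figure.** The documents give no number for this subgroup, so the design inputs are checked first. With hazard ratio 4.2/7.5 = 0.56, one-sided alpha 0.10, 80% power and 1:1 allocation, Schoenfeld's formula gives 4 × (1.2816 + 0.8416)² / (ln 0.56)² = 53.6, or 54 events against the stated 53; 53 events give 79.6% power. For both strata combined, 75 events at one-sided 0.05 give 80.7% against the stated 81%. The design figures reproduce. They supply the medians used below but do not bear on the point itself.

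**Inputs**
- From SAP section 4: control median PFS 4.2 months; hazard ratio 0.56, with 1.00 as the null case; 12 months' enrolment and 10 months' follow-up, hence censoring uniform from 10 to 22 months.
- From SAP 3.1: at most six platinum cycles of 21 days, so a switch window of 126 days, or 126/30.4 = 4.14 months.
- Assumed: exponential PFS; a constant switch hazard within the window, giving a 10% to 40% chance of switching in the absence of progression; switching unrelated to prognosis.

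**Method.** For each scenario, 400,000 cisplatin starters were simulated. A subject switched only while progression-free and inside the window. The Cox model with treatment alone was fitted to all starters and again without switchers.

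**Result.** Across scenarios, keeping all starters gave 0.997 to 1.005 for a true 1.00, and 0.558 to 0.565 for a true 0.56. Excluding switchers gave:

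| Assumed switch probability, control / patritumab | True HR 1.00 | True HR 0.56 | Share excluded at true HR 0.56, control / patritumab |
|---|---|---|---|
| 10% / 10% | 1.00 | 0.56 | 7% / 8% |
| 20% / 20% | 1.00 | 0.56 | 15% / 17% |
| 30% / 30% | 1.00 | 0.57 (0.565) | 22% / 25% |
| 20% / 30% | 1.04 | 0.59 | 15% / 25% |
| 10% / 30% | 1.06 | 0.60 | 7% / 25% |
| 20% / 40% | 1.08 | 0.61 | 15% / 34% |
| 30% / 20% | 0.97 | 0.55 | 22% / 17% |
| 40% / 20% | 0.93 | 0.53 | 30% / 17% |

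At 30% in both arms and a true 0.56, the median among those retained falls from 4.2 to about 3.6 months on control and from 7.5 to about 6.8 on patritumab.

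**Why equal switching does little to the ratio.** Among retained subjects the hazard at time t is the true hazard divided by the chance of not switching later. At time zero that chance is 1 minus the share excluded. With 30% in both arms it is 1 − 0.223 = 0.777 on control and 1 − 0.252 = 0.748 on patritumab. The ratio at the start is therefore 0.56 × 0.777/0.748 = 0.58, and it returns to 0.56 by the end of the window, so the average moves little. With 20% against 40% under a true 1.00, the starting ratio is (1 − 0.147)/(1 − 0.300) = 1.22, which averages to 1.08.

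**The case against.** The strongest reply is that this is small and unproven. It concerns one row among eleven exploratory factors, analysed only if the data support it. Subgroup noise is much larger than the shift. If 30 to 50 of the roughly 75 PFS events fall in the cisplatin group (an assumption; the split is not given), the standard error of the log hazard ratio is about √(4/50) = 0.28 to √(4/30) = 0.37. A 95% interval around 0.56 then has a lower limit of 0.27 to 0.32 and an upper limit of 0.97 to 1.15. A move from 0.56 to 0.61 is ln(0.61/0.56) = 0.086, or about 0.2 to 0.3 standard errors. This stands, and it keeps the point minor.

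Nor do the documents predict more switching on patritumab. The Phase 1b study of the combination saw no dose-limiting toxicities (Protocol 1.1.1.5). The main reactions named in Protocol 1.3 are diarrhoea, vomiting, rash and dry skin, whereas switching requires toxicity to cisplatin, and the one directed switch is for neuropathy. Switching is also decided under blinding. A reader might infer that the rule works against patritumab; the documents support no particular direction.

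A reader might also infer that longer PFS on patritumab is enough to bias the hazard ratio, since more of that arm stays at risk of switching: at 4.14 months, 2^(−4.14/7.5) = 68% are progression-free against 2^(−4.14/4.2) = 50% on control. The equal-rate rows show otherwise.

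Finally, the exclusion gives groups with a single platinum exposure, which has some descriptive value. That supports keeping it as a secondary display, not as the only analysis.

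**Conclusion.** The point holds as a minor one. A stated rule removes randomised subjects on a post-randomisation event, no alternative is given, and the table label suggests that nobody is missing. The effect is confined to the cisplatin row, because a carboplatin starter is meant to stay on carboplatin. The primary PFS test, the HRG strata and the error rate are untouched.

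The exclusion needs a between-arm difference in switching to bias the hazard ratio materially. Within the assumed 10% to 40%, the range is about 0.93 to 1.08 for a true 1.00 and 0.53 to 0.61 for a true 0.56. With equal switching, the costs are the lost subjects and the shortened medians. Confidence is high in the mechanism and low in these sizes, because the switch rates are assumptions and switching was taken as independent of prognosis; a link with prognosis could change the result. OS carries the same exclusion but was not simulated.

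It would also be too strong to infer that removing the exclusion would make cisplatin against carboplatin a fair comparison. The starting agent is the investigator's choice, so that contrast stays confounded under any rule.

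**What to change.** In SAP 8.2.4.2:
- Define the platinum subgroup by the first platinum agent administered, and keep switchers in that group.
- State what happens to subjects randomised but never dosed. SAP 6.3 keeps them in efficacy analyses, yet they have no first agent. Use the intended agent if it was recorded before randomisation; otherwise show them as not classifiable.
- Report the number of switchers by arm.
- Keep the version that excludes switchers only as a labelled sensitivity analysis.

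This takes a few lines of SAP text and changes no treatment. Administration is already recorded by drug (Protocol 5.1.2; SAP Listing 16.2.5.1.2). Protocol 6.1.3 does not mention recording the intended agent at randomisation, so that part depends on whether it was captured. The downside is that the cisplatin group will contain some subjects with mixed platinum exposure, including anyone switched early, and a few undosed subjects may stay unclassified.

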8.3. Safety Analyses

All analyses involving safety data (extent of exposure, TEAEs, clinical laboratory results, vital signs, ECG, echocardiograms/MUGAs, physical exam, HAHA, and ECOG performance status) will be performed on the Safety Analysis Set. No inferential statistical analysis is planned for safety data. Descriptive statistics will be calculated for quantitative safety data and frequency counts and percentages will be compiled for classification of qualitative safety data. All percentages will be calculated based on the number of subjects in the Safety Analysis Set. If the number of subjects with available data does not allow for the reliable estimation of variability at a scheduled time point, no summary statistics will be presented for that time point. Unless otherwise noted, baseline values will be the last non-missing assessment collected prior to first dose of study drug.

8.3.1. Adverse Events

A treatment-emergent AE (TEAE) is defined as an adverse event that has an onset date on or after the first dose of patritumab/Placebo, or worsens in severity after the first dose of patritumab/Placebo relative to the pre-treatment state. An adverse event that occurs more than 30 days after the last dose of study medication will not be included as a TEAE, unless it is considered drug related.

Adverse events will be coded using the Medical Dictionary for Regulatory Activities (MedDRA) and summarized for the number and percentage of subjects reporting treatment emergent AEs. AEs/toxicities and laboratory test results (hematology and blood chemistry) will be graded according to the NCI CTCAE, Version 4.03. The number and percentage of subjects reporting TEAEs will be tabulated by the worst CTCAE grade, system organ class, and preferred term with a breakdown by treatment group. Similarly, the number and percentage of subjects reporting treatment emergent serious adverse events (SAEs) will be tabulated, as well as TEAEs and treatment emergent SAEs considered related to patritumab, cetuximab, and cisplatin/carboplatin.

At each level of subject summarization, a subject will be counted once if he/she reports one or more occurrences of the same system organ class/preferred term/grade. For treatment-emergent (serious) adverse event toxicity tables tabulated on subject level, a subject with two or more treatment-emergent adverse events with the same preferred term will be counted only once for that term using the most severe toxicity. For a given subject, if the toxicity grade is missing for all treatment-emergent adverse events with the same preferred term, the treatment-emergent adverse events will be counted only once for that term under the "Missing" CTCAE toxicity category. In the presence of a subject who has both missing and non-missing CTCAE toxicity grades for adverse events with the same preferred term, the missing CTCAE toxicity of the adverse event will be treated as the lowest toxicity grade. In addition, a subject who reported two or more treatment-emergent adverse events with the same system organ class will be counted only once in the system organ class total, and subjects with two or more treatment-emergent adverse events in different system organ classes will be counted only once in the overall total.

A by-subject AE (including treatment emergent) data listing including, but not limited to, verbatim term, preferred term, system organ class, CTCAE grade, and relationship to study drug will be provided.

SAEs reported from tumor biopsies collected during Screening will be recorded, but not included in the primary analysis.

Deaths, other SAEs, and other significant AEs, including those leading to permanent discontinuation of subjects from patritumab, cetuximab, and cisplatin/carboplatin will be listed.

